We estimate that 25% of screened patients will not meet eligibility criteria, which means that at least 300 patients will be screened.

d) Study Timelines

Subjects will be enrolled during their hospital stay and will participate in the study for 3 months following hospital discharge. The intervention will be delivered during the 4 weeks following discharge. Final assessment for outcomes will be performed at 3 months after discharge. We anticipate enrollment will occur between July and December of 2019. We estimate that primary analyses will be completed by June of 2020.

e) Study Endpoints

The primary outcome will be the number of initial hospital readmissions within 30 days of discharge. Secondary outcomes will also be assessed at 30 days of discharge unless otherwise specified. Secondary outcomes will include:

1. time to first readmission
2. number of emergency department (ED) visits
3. a composite of 30d readmissions and ED visits

Readmission Pilot Trial

4. number of primary care and specialist provider follow-up visits scheduled and attended
5. incidence of medication review or reconciliation post-discharge
6. cost of post-discharge care as a sum of ED visits, readmission, home health services, and outpatient provider visits
7. cost of the intervention
8. subject experience assessed by a brief questionnaire
9. self-monitored blood glucose levels and frequency of testing
10. change in well-being from baseline to 5 weeks after discharge as measured by the World Health Organization Well-Being Index (WHO-5).[43]
11. change in diabetes-related distress at 5 weeks after discharge as measured by the Problem Areas in Diabetes (PAID) scale.[44]
12. change in perceived social support at 5 weeks after discharge as measured by the Multidimensional Scale of Perceived Social Support (MSPSS).[45]
13. change in perceived stress at 5 weeks after discharge as measured by the perceived stress scale (PSS).[46]
14. change in diabetes knowledge at 5 weeks after discharge as measured by the Diabetes Knowledge Test (DKT2).[47]
15. change in A1c level from baseline to 3 months after the index discharge

f) Procedures Involved in the Human Research

After enrollment, subjects will be sorted into 2 groups based on the predicted risk of readmission by the DERRI: high risk and low risk (Figure 1).

[figure not shown]

Figure 1. Allocation of study participants

Low-risk group:

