Adverse events								X
Low-risk group								
Chart review/phone call								X
Psychometric assessments	X							X
Diabetes knowledge	X							X
A1C	X							X
30d endpoints								X

Readmission Pilot Trial

of follow-up appointments, confirming access to medications, and answering questions.

Data collection: The following data will be collected at baseline: A1c, sociodemographics, medical history, including HIV, substance abuse, and mental health status, which are likely risk factors for admission, relevant laboratory results, admission diagnoses, self-reported goals for health and diabetes, well-being (WHO-5), diabetes-related distress (PAID scale), perceived social support (MSPSS), perceived stress (PSS), diabetes knowledge (DKT2), depression screening by the PHQ-2/9, and health literacy by the BHLS (Table 2).

The following data will be collected during follow-up: A1c, discharge diagnoses, hospital readmission (date, primary diagnosis), ED visits (date, primary diagnosis), physician follow-up appointments scheduled and/or attended, post-discharge medication reconciliation (yes/no), cost of post-discharge care, self-monitored blood glucose levels, Nurse Navigator time to deliver the intervention (minutes), well-being (WHO-5), diabetes-related distress (PAID scale), perceived social support (MSPSS), perceived stress (PSS), diabetes knowledge (DKT2), depression (PHQ), and patient experience according to a brief questionnaire (**Appendix Item 3a [usual care] or 3b [intervention]**). These follow-up data will be collected during a phone call about 5 weeks after the index discharge. Baseline and 3-month post-discharge A1c levels will be obtained as part of standard-of-care. A letter reminding patients to do the 3-month blood draw for the A1c test will be sent by mail.

Data will be collected by phone interviews with subjects and review of the electronic medical record (EMR). The Research Specialist will be primarily responsible for screening and recruiting subjects, data collection and data entry.

Phase B: Qualitative evaluation of intervention

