All data collected by the research team will be considered part of the participant's confidential record. Data collected on paper from research participants will be placed in a locked file cabinet in the GCRC within 24 hours. The destruction date of paper files will be at least 7 years from the termination of the study and will be authorized by the PI. Access to research and confidential records will be limited to clinical investigators and research coordinators.

h) Data Management

Statistical analysis: Distributions of the data will be assessed by descriptive statistical and graphical methods. To assess the randomization procedure, baseline values of all variables will be compared between the intervention and usual care group. Between-group differences for continuous variables will be compared using the Wilcoxon test. Proportions will be compared between groups using the chi-square test or exact tests when expected cell counts are less than 5. The primary outcome of 30d readmission rate will be compared between intervention and control groups with the chi-square test. Point estimates of 30d readmission rates will be obtained and presented with 95% confidence intervals. Time to readmission will be estimated by Kaplan-Meier curve and compared between groups by log-rank test. The composite of 30d readmission and ED visits will be compared by Cox regression model. Continuous secondary outcomes will be compared using Wilcoxon test. Categorical secondary outcomes will be compared using chi-square test. The primary analyses for all outcomes will be performed in the intention-to-treat (ITT) population. Secondary analyses for all outcomes will be performed in a per-protocol population restricted to subjects who complete at least one follow-up phone call. In addition, outcomes will be assessed for differences by the number of follow-up phone calls

Readmission Pilot Trial

completed (dose-response analysis). Lastly, all outcomes will be assessed in the ITT subgroup of subjects with a baseline A1c >7%. Statistical significance will be claimed at an alpha level of 0.05.

Power analysis: The sample size for Phase 2A was based on an expected drop-out and post-enrollment exclusion rate of 25% as well as the capacity of the research team. Because this is a pilot feasibility trial, the study is not powered to detect a difference in outcomes.

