Data Entry Requirements: All data will be coded by the research assistant prior to entry. The research assistants will maintain a log of any reviewed data issues so that future occurrences of problems will be handled in the same manner. The data entry system (REDCap) will require a login identification and password to gain access to the data. When appropriate, validation and range rules will be applied to the actual entry fields. Only the research assistants will be able to view the data in its raw state. All other authorized personnel (i.e. the PI, statistician and Data Safety Officer) will view data via forms and reports created by the research assistants.

Audit/Verification of Entered Data:

Primary Outcome Data: Data designated as primary outcome date (i.e., presence or absence of 30d readmission) will be subject to a 100% cross-reference check with original hard copies. This audit must have an error rate less than 0.5%. If the verification fails the audit, all data will be re-entered, the original computer files discarded, and the newly re-entered data audited. This process will continue until the audit no longer exceeds the maximum allowable error rate. All audits will be supervised and documented by the study's research assistant.

All Other Information: All other entered information will be subject to a 20% sample that will be cross-referenced with the original paper copy. This audit must have an error rate less than 0.5%. If the sample fails the audit, all data will be verified against the paper originals. If the error rate of the complete audit is greater than 0.5%, all data will be re-entered, the original computer files discarded, and the newly re-entered data audited. This process will continue until the audit no longer exceeds the maximum allowable error rate. At the discretion of the PI, the full audit may be omitted in favor of a complete re-entry of the original paper data. All audits will be supervised and documented by the research assistant.

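### Death after discharge is in no endpoint and on neither follow-up data list, so a 30-day death without a return to hospital is scored as not readmitted or lost as a drop-out

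*Protocol*

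**What the plan says.** - **Endpoints (section 8 e).** "The primary outcome will be the number of initial hospital readmissions within 30 days of discharge". The 15 secondary outcomes include time to first readmission, the number of ED visits and "a composite of 30d readmissions and ED visits". None includes death.
- **Coding (section 8 h, audit of entered data).** The primary datum is the "presence or absence of 30d readmission", a two-state field.
- **Analysis (section 8 h, statistical analysis).** "The primary outcome of 30d readmission rate will be compared between intervention and control groups with the chi-square test". Also: "The primary analyses for all outcomes will be performed in the intention-to-treat (ITT) population". For the time-to-event outcome: "Time to readmission will be estimated by Kaplan-Meier curve and compared between groups by log-rank test". The composite is compared by Cox regression.
- **Follow-up data, randomized groups (section 8 f, Phase A, data collection).** "The following data will be collected during follow-up: A1c, discharge diagnoses, hospital readmission (date, primary diagnosis), ED visits (date, primary diagnosis), physician follow-up appointments", and so on through costs, glucose, questionnaires and patient experience. Vital status and date of death are not listed. The shorter list for the low-risk group has the same gap.
- **Where death does appear.** Death during the index stay is exclusion 5 in section 8 b). A fatal event meets the seriousness definition in section 8 j), but that section confines adverse events to problems arising from a study assessment or from the intervention.

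**The concern.** Death before a first readmission makes that readmission impossible. A two-state outcome in an intention-to-treat denominator has no place for it. On the protocol's definition, a subject who dies at home on day 6 has no readmission. If the subject is instead dropped because the 5-week call cannot be completed, the denominator changes. Either way the death does not appear beside the primary result.

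This matters even in a pilot. Aim 1 includes efficacy, section 8 h) sets a significance level of 0.05, and the results are meant to guide a definitive trial. Management after discharge also differs by design: only the intervention arm has its diabetes therapy set by the study algorithm and receives the Navigator calls. If early deaths differed between arms, in either direction, the readmission comparison would be distorted and the listed follow-up data might not show it.

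**Working it through.** The protocol states no power or event figure that depends on this point, so there is no figure of its own to reproduce. The check has two parts.

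**1. Could a death be recorded by another route?**

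- *Adverse-event reporting.* A fatal event linked to the intervention would be reported. A death from the illness that caused the admission does not clearly meet the definition. Table 2 marks adverse events six times for the intervention group and once for usual care, and has no adverse-event row for the low-risk group. Ascertainment by this route could therefore differ between arms.
- *Medical record and phone call at about 5 weeks.* These may bring some deaths to light, but neither data list has a field for them.
- *Exclusion 5.* This covers the index stay only.

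**2. How much can it move the comparison?**

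Inputs from the protocol: 60 per randomized arm (section 8 c) and 25% drop-out and post-enrollment exclusion (section 8 h), leaving 60 × 0.75 = 45 per arm.

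Shift in the arm difference for each excess death in one arm, when it is scored as a non-event rather than an event:

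- n = 60: 100/60 = 1.7 points
- n = 45: 100/45 = 2.2 points

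Illustration with assumed counts: 18/60 readmitted under usual care, 12/60 under the intervention, and three intervention deaths without readmission against none under usual care.

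| Handling of the deaths | Usual care | Intervention | Difference |
|---|---|---|---|
| Not readmitted | 18/60 = 30.0% | 12/60 = 20.0% | 10.0 points |
| Drop-out | 18/60 = 30.0% | 12/57 = 21.1% | 8.9 points |
| Counted as events | 18/60 = 30.0% | 15/60 = 25.0% | 5.0 points |

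With one death in each arm, counting deaths as events gives 19/60 against 13/60, still 10.0 points. Balanced deaths leave the difference unchanged.

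A second assumed case shows the effect on a significance claim (chi-square without continuity correction). Readmissions of 18/60 against 8/60 differ by 16.7 points, p = 0.027. With 0 against 3 deaths added as events, 18/60 against 11/60 differ by 11.7 points, p = 0.136.

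**How likely is at least one such death?** The protocol gives no rate. I assume that m = 1% to 5% die within 30 days without readmission.

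- Expected number per arm, 60 × m: 0.6 at 1%, 3.0 at 5%
- Chance of at least one among the 120 randomized, 1 − (1 − m)^120: 70% at 1%, 91% at 2%, over 99% at 5%

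**The case against.** The strongest reply is that readmission and ED use are the trial's declared targets, that handling of death is usually left to the statistical analysis plan, and that serious deaths are reportable anyway. Much of this stands.

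- **Analysis plan.** It may well say whether a death is a non-event, missing, censored or competing. But endpoint content and the follow-up data lists are fixed in the protocol, and an analysis plan cannot analyze deaths that were not collected.
- **Safety reporting.** A death attributed to the intervention would be reported and seen by the Data Safety Officer. The definition leaves open deaths from underlying illness.
- **Likely size.** Exclusions for palliative care, hospice, long-term care and transfer, and entry limited to non-critical-care units, may put the death rate near the low end of the assumed range. A death preceded by an ED visit is already an event in the composite. The study is declared as not powered on outcomes.

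Four stronger readings are tempting, and the protocol does not support them:

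1. *That deaths are counted as treatment successes.* The protocol nowhere says so. Scoring as not readmitted follows from the definition, and loss as a drop-out is equally possible.
2. *That validation of the DERRI under Aim 2 is biased.* The tool predicts all-cause readmission. A patient who died at home was not readmitted, so scoring no readmission is right for that target.
3. *That the treatment comparison is biased by 1 to 5 points.* That range is the shift in one arm's rate under the assumed death rates. Only an imbalance between arms biases the difference.
4. *That the log-rank and Cox analyses are invalid.* With censoring at death they remain valid comparisons of the cause-specific hazard. Only one minus the Kaplan-Meier estimate, read as an absolute risk of readmission, comes out too high.

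**Conclusion.** The point holds as a gap in endpoint content and data collection. The protocol neither lists death after discharge as something to record nor gives it a place in the primary outcome. The consequence for the arm comparison is conditional: none if deaths without readmission are balanced, and 1.7 points per excess death at 60 per arm (2.2 at 45) if they are not. An imbalance of a few deaths could halve an apparent 10-point difference, as the assumed counts show. How probable that is cannot be derived from the protocol, because it gives no death rate; the 1% to 5% range is an assumption. The change should be made because it is cheap and the data may be hard to recover later. It does not affect the sample size, and it is not a reason to replace the primary outcome or redefine the composite, which follow Aim 1 as they stand.

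**What to change.** - Add vital status and date of death to the 5-week record review and phone call in all three groups, ascertained in the same way in each.
- Keep 30-day readmission as the primary outcome and the readmission/ED composite as stated. Say explicitly that a subject who dies without readmission stays in the intention-to-treat denominator.
- Report deaths without readmission by arm, beside the primary result.
- Add one sensitivity comparison of readmission or death within 30 days, using the same chi-square test.
- Show time to readmission as cumulative incidence with death as a competing event. The log-rank test and Cox model may stay, labeled as cause-specific comparisons.

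Cost: one extra data item at a contact already planned, one extra table row, one extra comparison and a changed display for one curve. No change to sample size or schedule.

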4) Post-discharge support: At 24 to 48 hours post-discharge, a nurse Navigator will call the patient to assess the patient’s status, confirm receipt of and compliance with medications, verify the follow-up appointment schedule, assess for barriers to following the discharge plan, determine the need for a community health worker (CHW) referral, and review blood glucose control (patients who are discharged on non-insulin regimens will be expected to test their blood glucoses at least once a day, and patients who are discharged on an insulin regimen will be expected to test their blood glucoses at least twice a day). Similar phone calls will be made weekly for four weeks following discharge by a Navigator. If a patient reports significant high or low blood glucose levels, then the PI or a co-Investigator (Endocrinologists) will call the patient to adjust diabetes therapy (See Tables 1a and 1b for insulin dose adjustment protocols). Eligible patients will receive a referral for a nursing visit from a local home care agency to assess medical needs for support at home and medication reconciliation. Referral to a CHW may be made if subjects are found to have non-medical needs and/or obstacles to maintaining self-care and attending follow-up appointments. Such non-medical support might include transportation to and from medical appointments, food, housing, or legal assistance, relief from utility bills, verification of insurance, support groups and delivery of durable medical equipment.

Table 1a. **Outpatient basal insulin dose adjustment:**

Basal Insulin	
If mean FBG > 180 mg/dL for the last 2 consecutive days and no episodes of hypoglycemia	Increase daily basal dose by 4 IU
If mean FBG > 140 mg/dL for the last 2 consecutive days and no episodes of hypoglycemia	Increase daily basal dose by 2 IU
If mean FBG between 100 to 140 mg/dL for the last 2 consecutive days and no episodes of hypoglycemia	No Change
If any FBG between 70 – 99 mg/dl	Decrease by 4 IU or 10% of total daily basal dose
If any FBG < 70 mg/dl	Decrease by 8 IU or 20% of total daily basal dose
If any FBG < 40 mg/dl	Decrease total daily basal dose by 30%

FBG=Fasting blood glucose; Hypoglycemia=typical symptoms (e.g., sweating, tremor, acute hunger, anxiety) and/or blood glucose <70 mg/dL

Table 1b. **Outpatient prandial/pre-meal insulin dose adjustment based on subsequent mealtime/HS BG values:**

Pre-meal Rapid Insulin		
Pre-meal Dose, U	BG 70 – 100 mg/dl*	BG 141-180 mg/dl**

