≤ 10 U	Decrease by 1 U	Increase by 1 U
>11- 19 U	Decrease by 2 U	Increase by 2 U
≥ 20 U	Decrease by 3 U	Increase by 3 U
Pre-meal Dose, U	BG 40-70 mg/dl x 1	BG 180-240 mg/dl x 1

Readmission Pilot Trial

≤ 10 U	Decrease by 2 U	Increase by 2 U
>11- 19 U	Decrease by 3 U	Increase by 3 U
≥ 20 U	Decrease by 4 U	Increase by 4 U
Pre-meal Dose, U	BG < 40 mg/dl x 1***	BG > 240 mg/dl x 1
≤ 10 U	Decrease by 4 U	Increase by 3 U
>11- 19 U	Decrease by 6 U	Increase by 4 U
≥ 20 U	Decrease by 8 U	Increase by 5 U

Pre-meal insulin dose adjustment is based on the subsequent BG value, e.g., pre-breakfast insulin dose is based on the pre-lunch BG.

* If > ½ of the mealtime/HS BG values for the week were below target.

**If > ½ of the mealtime/HS BG values for the week were above target.

*** Decrease by 30-40% in the event of severe hypoglycemia (mealtime/HS BG < 40 mg/dl).

BG=blood glucose; Mealtime/HS=pre-lunch, pre-dinner, or bedtime

The above algorithm provides recommended insulin doses and may be modified based on clinical judgment of the investigator or co-investigator.

Usual care: Most aspects of the intervention go above-and-beyond usual care. Patients in the usual care group will receive the standard discharge instructions and medication reconciliation process. Those who are new to diabetes receive training by a floor nurse on using a glucometer as well as a stock set of printed educational materials. The floor nurses also train patients who are new to insulin injections as needed. Patients with diabetes are referred to outpatient diabetes education at Temple on a case-by-case basis as determined by the primary hospital provider team. Diabetes therapy upon discharge is decided on a case-by-case basis by the primary team. Discharge instructions are routinely sent to the primary care physician either by fax or EPIC. Most TUH patients receive a phone call 2 to 4 days after discharge from a CHW that includes checking on the status

Table 2. Timeline for assessments of subjects

Visit #	1	2	3	4	5	6	7	8
Time (weeks)	0	2 days	1	2	3	4	5	13
Intervention group								
Phone call/clinic visit								X
Psychometric assessments	X							X
Diabetes knowledge	X							X
30d endpoints								X
Interview							X	
A1C	X							X
Navigator call		X	X	X	X	X		
Blood glucose		X	X	X	X	X	X	
Adverse events		X	X	X	X	X	X	
Usual care group								
Phone call								X
Psychometric assessments	X							X
Diabetes knowledge	X							X
30d endpoints								X
A1C	X							X
Blood glucose								X

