- All data linking subjects to de-identified information will be maintained in a password-protected, encrypted computer with access limited to only those research personnel with a reasonable need to have such information.
- Reporting Adverse Events
 - Definitions:
 - Adverse Event: Any medical problem that manifests during the course of the study, as a result of an assessment or an aspect of the study intervention.
 - Serious Adverse Event: An adverse event that is fatal or life-threatening, results in significant or persistent disability, or requires hospitalization.
 - Unexpected Serious Adverse Event: Any event that has not been described in the protocol or informed consent document.
 - Reporting Mechanisms
 - All adverse events will be discussed at weekly operations meetings and reported to the PI and IRB according to standard operating procedure.
 - Serious adverse events (expected and unexpected) will be reported to the PI immediately and to the IRB in writing within 1 business day.
 - The NIH procedure for Reporting Clinical Study Serious Adverse Events will be followed for the reporting of expected and unexpected serious adverse events to the study sponsor.
- The DSO will review the protocol and study procedures every 3 months to ensure that proper regulatory processes are followed during study execution. In this role, he will:

Readmission Pilot Trial

- Review all adverse events or complications related to the study and make recommendations for protocol changes if indicated.
- Assure scientific integrity of the study by providing regulatory oversight.
- Assure participants' confidentiality and informed consent by reviewing study procedures.
- Provide advice, as requested, on quality assurance measures.

k) Withdrawal of Subjects

Subjects may withdraw at will at any time. Subjects may be withdrawn from the trial at the discretion of the PI due to a safety concern, if judged non-compliant with trial procedures, or pregnancy during the primary follow-up period (30 days after discharge). For subjects in the intervention group, we will obtain permission to continue to collect data from the electronic medical record.

9) Risks to Subjects

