The study involves low risk from interviews and the intervention, which entails education, coordination of care, and post-discharge support. A1c-based adjustment of diabetes therapy poses the usual risk of hypoglycemia associated with diabetes therapy. However, only patients with uncontrolled diabetes according to an elevated A1c will have their diabetes therapy adjusted. Patients will be followed closely for 30 days after discharge and glycemic control will be monitored. Because the study will only be using FDA-approved medicines and checking routine A1C blood tests, it is unlikely that costs will be more than if a doctor was managing the subject outside the study.

10) Potential Benefits to Subjects

Participants in the intervention may have a lower risk of readmission and improved glycemic control with 30 days of discharge.

11) Privacy and Confidentiality

The study will use PHI and a HIPAA Authorization has been submitted. Paper data collection records with personal identifiers will be stored in locked file cabinets. Electronic data will not include personal identifiers other than the unique study ID. Audio files for the in-depth interviews will be stored on the research assistant's password-protected computer and erased from the digital recorder after storage. Access to research and confidential records will be limited to clinical investigators and research coordinators. All data linking subjects to de-identified information will be maintained in a password-protected, encrypted computer with access limited to only those research personnel with a reasonable need to have such information. Staff will be trained to collect data for the study and maintain participants' confidentiality. Interviews with subjects will be conducted in private. Presentation of the study results at regional or scientific meetings or in publications will not identify subjects.

12) Compensation for Research-Related Injury

If study volunteers sustain injury as a result of their participation in this study, they will be advised to seek immediate medical attention. However, there is no commitment by Temple University, Temple University Health System or its subsidiaries to provide monetary compensation or free medical care in the event of a study-related injury. The study volunteers have not waived any of their legal rights which they would otherwise have as a participant in an investigational study.

13) Economic Burden to Subjects

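### The adverse-event definition in section 8 j) admits hypoglycemia on study-adjusted therapy but not on usual-care therapy, so by-arm counts of the one named treatment risk are not comparable

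*Protocol*

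**What the plan says.** - **The risk.** Protocol section 9: "A1c-based adjustment of diabetes therapy poses the usual risk of hypoglycemia associated with diabetes therapy". It is the only treatment risk named there.
- **The outcomes.** Section 8 e) lists one primary and 15 secondary outcomes. None names hypoglycemia. Item 9 is "self-monitored blood glucose levels and frequency of testing".
- **The definition of hypoglycemia.** The protocol has one, in the footnote to Table 1a on insulin titration: "Hypoglycemia=typical symptoms (e.g., sweating, tremor, acute hunger, anxiety) and/or blood glucose <70 mg/dL".
- **The adverse-event rule.** Section 8 j): "Any medical problem that manifests during the course of the study, as a result of an assessment or an aspect of the study intervention". A serious adverse event is defined as an adverse event meeting further criteria, so it carries the same restriction.
- **Control therapy.** Section 8 f), usual care: "Diabetes therapy upon discharge is decided on a case-by-case basis by the primary team".
- **The schedule.** Table 2 has an adverse-event row for both randomised arms, with six marks for the intervention and one for usual care.
- **Data already collected in both randomised arms.** Section 8 f), data collection: "hospital readmission (date, primary diagnosis), ED visits (date, primary diagnosis"). The same paragraph says: "These follow-up data will be collected during a phone call about 5 weeks after the index discharge".

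**The concern.** An adverse event here must be caused by the study. Only one arm receives study-directed diabetes therapy, so the same low glucose reading can be an adverse event in the intervention arm and nothing in usual care. Yet Table 2 calls for an adverse-event check in usual care, under a definition that shuts out the event most relevant to the comparison.

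Phase B and the team's experience are meant to shape a definitive trial. A listing with several hypoglycemia events in one arm and none in the other could be misread as a safety signal when the recording rule alone produced it. An analysis plan written later can choose how to tabulate events, but it cannot recover events that were never recorded.

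**Working it through.** The point turns on the text, and the plan states no figure to reproduce. The check has four steps, and only the last involves arithmetic.

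**1. Does any listed outcome cover hypoglycemia?** Reading the 1 + 15 = 16 outcomes in section 8 e), none does by name or by threshold. Item 9 collects glucose levels, from which low readings could be derived. However, a daily testing expectation is stated only for the intervention, for example "patients who are discharged on an insulin regimen will be expected to test their blood glucoses at least twice a day". Counts of low readings would therefore depend on how often each arm tests.

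**2. Does the adverse-event route cover it alike in both arms?**

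| | Intervention | Usual care |
|---|---|---|
| Who sets diabetes therapy at discharge | Study endocrinologists | Primary team |
| Is that therapy an aspect of the study intervention? | Yes | No |
| Hypoglycemia on that therapy meets section 8 j)? | Yes, when attributed to the intervention | No |
| Adverse-event marks in Table 2 | 6 | 1 |
| Blood glucose marks in Table 2 | 6 | 1 |
| 30-day endpoint marks in Table 2 | 1 | 1 |

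The counts use the number of marks per row and do not rely on column position. The third row of the table is the substance of the point: the rule differs by arm. The extra contacts in the intervention arm push the same way, but they belong to the intervention.

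**3. Is there a source that treats the arms alike?** Yes. The date and primary diagnosis of every readmission and ED visit are collected in both randomised arms. Hypoglycemia coded as the primary diagnosis of an acute visit can therefore be counted on the same footing without new data.

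**4. How precise would that count be?** With no events in n subjects, the exact two-sided 95% upper limit is 1 − 0.025^(1/n).
- n = 60 (planned arm size, section 8 c): 1 − 0.025^(1/60) = 0.0596, or 6.0%.
- n = 45, after the 25% loss expected in section 8 h), 60 × 0.75 = 45: 1 − 0.025^(1/45) = 0.0787, or 7.9%.

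The size of the distortion in step 2 cannot be computed. It needs a hypoglycemia rate and the share of intervention events attributed to the study, and the protocol gives neither.

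**The case against.** The strongest reply is that section 8 j) is a reporting rule for the IRB and the funder, not an endpoint definition. The aims are feasibility, acceptability, efficacy and validation of the risk score, and a comparative safety estimate is not among them. Section 8 h) plans no between-arm adverse-event test and disclaims power. The usual-care check in Table 2 could be meant only for problems arising from study assessments. Appendix Items 3a and 3b, the follow-up questionnaires, are not shown and might already ask about hypoglycemia.

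Much of this stands, and it rules out several stronger readings that a reader might infer:

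- *That the trial has no like-for-like information on hypoglycemia.* It has some: acute visits with their primary diagnosis are collected alike in both arms.
- *That the absence of hypoglycemia from section 8 e) is itself an error.* It contradicts no stated aim, and tabulating low readings could be left to an analysis plan. A named line would be an addition.
- *That the six-to-one schedule is a flaw.* Weekly calls are part of the intervention, and closer monitoring is proper where study physicians change therapy.
- *That the bias has a known size.* One could assume 6 true cases per arm of 60, every intervention case attributed and no control case recorded. That gives 6 v 0, a 10-point difference, which only restates the assumption.

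What the reply does not remove is the recording rule. If the usual-care check is only for assessment-related problems, hypoglycemia on usual-care therapy is excluded by design, and any by-arm listing remains lopsided.

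**Conclusion.** The point holds as a matter of recording. Under section 8 j) as written, hypoglycemia on study-adjusted therapy can be an adverse event and hypoglycemia on usual-care therapy cannot. By-arm adverse-event counts for the one treatment risk the protocol names are therefore not comparable, and the expected direction is against the intervention.

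This assumes that staff apply the definition literally and that at least some intervention-arm events are attributed to the therapy adjustment. The primary outcome and the planned tests are unaffected. It is a modest improvement, worth making because it is cheap and cannot be made after the events have gone unrecorded.

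**What to change.** 1. **Section 8 j).** Add a sentence: hypoglycemia, as defined under Table 1a, is recorded in both randomised arms regardless of cause. Ask the same question about the first 30 days after discharge in both arms at the existing 5-week call. Keep low readings found at Navigator calls for safety monitoring, outside the by-arm count.
2. **Reporting.** Give, by randomised arm, the number and proportion with a 30-day readmission or ED visit whose primary diagnosis is hypoglycemia, with exact 95% confidence intervals. Present this descriptively, and read it before the self-reported count.

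The cost is one changed sentence, one question at a planned call and one tabulation of data already collected.

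The limits should be stated with the results. Events will be few and intervals wide, as the 6.0% limit at zero events shows. A primary diagnosis misses episodes treated at home or coded as secondary. Self-report may still run higher in the intervention arm, because its discharge education teaches patients to recognise hypoglycemia. That is why the acute-visit table comes first.
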